8.1.2 Data listings

Electronic case report form (eCRF) and diary data will be listed as documented as well as all relevant generated and transformed variables next to the original data items. In all listings, cohort and analysis population for each patient will be included. The listings will be sorted by cohort and patient identifier.

The number and percentage of subjects screened, allocated to a cohort, received IMP, completed the full course of the trial and discontinued prematurely (incl. reasons for premature discontinuation) will be summarized by cohort and overall. Demographic data and all other baseline characteristics and the eligibility of patients will the summarized by cohort and overall.

eligibility of patients will be summarized by cohort and overall for the SAF and the FAS.

Medical history and concomitant diseases 8.3

Medical history and concomitant diseases will be coded using the MedDRA dictionary in the version and the update strategy as defined in the coding guideline for this study. A concomitant disease is defined as any diagnosis, for that either no stop date was documented or the stop date is later than day 1. Incomplete stop dates will be estimated using the last possible date in order to define whether a disease is concomitant.

Summary tables presenting number and percentage of patients with medical history and with concomitant diseases by MedDRA system organ class (SOC) and MedDRA preferred term (PT) will be provided cohort and overall for the SAF and the FAS. In these tables, SOCs and PTs within SOCs will be ordered with decreasing frequency in the total column.

Previous and concomitant medication 8.4

Prior and concomitant medications excluding FVIII treatments will be coded using the WHO drug dictionary Enhanced Version, in the version and using the update strategy as specified in the coding guideline for this study. Previous medication is defined as medication that started and stopped prior to Day 1 Concomitant medication is defined as medication with at least one dose taken after Day 1. Incomplete start dates will be estimated using the first possible date, incomplete stop dates will be estimated using the last possible date in order to define whether a treatment was taken concomitantly. For missing start dates, a start prior to Day 1 will be assumed.

If the treatment of a BE at one site is interrupted for more than 48 hours, the events are recorded and will be analyzed as two separate BEs; if another than the original bleeding site is affected, the events are recorded and will be analyzed as separate BEs at any time.

If there are several simultaneous bleeding sites, each bleeding site is recorded and will be analyzed as a separate BE.

For certain major bleeding events, e.g., iliopsoas bleeds or bleeding into target joints, it may be necessary to continue treatment beyond the resolution of the acute phase to prevent recurrent hemorrhage. These additional treatments should be recorded in the diary (and eCRF) but will not be evaluated as treatments of the BE.

ISSION

All efficacy ratings assessed as either 'excellent' or 'good' will be considered 'successfully treated.'

8.6.3 Analysis of BEs

For the current planned analysis of cohorts 1 to 5, the analysis as described below will not be performed since the daily dosing period had to be interrupted and then fully stopped due to inhibitor formation.

All bleeding episode will be presented for each patient in the trial, with a clear flag, whether the bleeding occurred prior to, during, or after the 3-month daily dosing period with OCTA101

All time periods of prophylactic treatment and all bleeding episodes during the 3-month daily prophylactic part will be pooled as y (number of BEs) and t (the pooled time intervals in days).

The total annualized bleeding rate is defined as $\lambda_{year} = y^*t/d$, with d = 365.25 days, a standardized year.

The spontaneous annualized bleeding rate, the traumatic annualized bleeding rate, the total annualized treated bleeding rate, the spontaneous annualized treated bleeding rate, and the joint annualized bleeding rate will be calculated in the same way, by restricting the count of bleedings to the respective type of bleeding.

In addition, the prior total annualized bleeding rate of patients who entered the 3-month daily prophylactic treatment based on all bleedings reported during the 6 months prior to the first dose of OCTA101 will be calculated in the same way and presented.

All other data collected for BEs and the efficacy assessments at the end of BEs will be analyzed descriptively. The analysis will be stratified by the product that was used to treat the bleeding, if applicable.

The proportion of BEs successfully treated with Human-cl rhFVIII and (if applicable) successfully treated with OCTA101 will be presented.

8.7 Diary data

All diary data collected will be analyzed as described in the other sections of the SAP. Data from diaries will be merged together with the data from the eCRF prior to the statistical analysis.

8.8 Safety

Safety and tolerability data will first be analyzed for each cohort after the first dose(s) and evaluated by an external DMC.

All safety and tolerability parameters (adverse events, vital signs, laboratory monitoring, and physical examination results) will be listed by patient and cohort.

Analyses based on data from repeat dosing from Cohort 1, 2, and 3 with OCTA101 for 3 months will be analyzed separately from data related to the first doses. In these analyses, data will be presented by cohort and overall. The analyses will thus be based on the SAF and the FAS.

8.8.1 Study drug exposure

Study drug exposure during the PK part of the study will be analyzed by cohort and by study drug for cohort 3.

Summary tables of number of injections, total dose applied in IU and in IU/kg will be presented by cohort and PK visit.

The following data will be presented for the treatment with OCTA101 during the daily 3-month treatment period by cohort and overall:

- .
- •
- •

Average dose (in IU/kg) and in absolute IU per week of OCTA101 Average dose (in IU/kg) and in absolute IU per injection of OCTA101 Average dose (in IU/kg) and in absolute IU per injection for each visit during the daily 3-month treatment period The number of injections per exposure day during the daily 3-month treatment period will be calculated as the number of injection sites when one vial was used and as the number of vials when more than one vial was used. Further, summary tables of total dose applied in IU and in IU/kg will be presented by cohort and overall for each visit during the daily 3-month treatment period.

All available data of study drug exposure will be listed.

- Embolic and thrombotic events, venous (SMQ)
- Embolic and thrombotic events, arterial (SMO) •
- Embolic and thrombotic events, vessel type unspecified and mixed arterial and venous (SMQ)

Local injection site reactions will be identified directly via the CRF entry (tickbox).

8.8.4 Local injection reactivity

Patients will evaluate injection site pain using a visual analog scale (VAS) from "0 mm/no pain" to "100 mm/extreme pain" immediately after injection completion. The local injection reactivity after single injections in the PK part will be summarized descriptively by cohort and PK visit and by overall for the follow-up PK visits.

The summaries will be provided stratified by injection site (abdomen or thigh) and by number of daily injections and overall.

Investigator (and patient in case of home treatment) shall assess local injection reactivity directly after injection and at 15 ± 5 min post-injection as described in ISO10999-10 standard:

- 0=no skin reactivity;
- 1=mild (subject is aware of the signs/symptoms, but finds it easily tolerated)
- 2=moderate (discomfort enough to cause interference with usual activities)
- 3=severe (subject is incapacitated and unable to work or participate in many or all usual activities).

For the injections during the daily 3-month treatment with OCTA101, the frequencies of local injection reactivity ratings by the investigator and the patient directly after injection and 15 ± 5 min post-injection will be summarized over the whole 3-month period using the number of injections as denominator. Visual analogue scale assessments of injection site pain will be summarized analogously.

8.8.5 Safety laboratory

Safety laboratory parameters will be analyzed using descriptive statistics for measured values at each visit and time point and for changes from pre-dose values prior to each single injection of OCTA101 for the SAF and the FAS.

8.8.6 Vital signs

Vital sign parameters will be analyzed using descriptive statistics for measured values at each visit and time point and for changes from pre-dose values prior to each single injection of OCTA101 for the SAF and the FAS.

8.8.7 Physical examination

Physical examination data will be displayed in patient data listings only.

8.9 Pharmacokinetic data

ermission In general for the analysis, non-quantifiable pre-dose levels will be set equal to zero. In the event of quantifiable levels prior to dosing, the baseline level will be subtracted from the post-dosing values and the further analysis is focused on the post-dosing changes from baseline.

All data collected at unscheduled visits will be not used in the PK analysis.

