## 9.2.2 Efficacy Analysis Plan

Property

Pharmacokinetic data will be analysed separately for each dose cohort.

Blood for the determination of the concentrations of FVIII:C (one-stage and chromo-genic assays) and OCTA12 in plasma will be sampled at scheduled times. The time courses of the plasma concentrations will be analysed non-compartmentally using the following conventions:

• The courses of the concentrations are analysed individually relative to the actual time of sampling (relative to the time of first injection).

- For the analysis, non-quantifiable pre-dose levels will be set equal to zero. In the event of quantifiable levels prior to first dosing, the baseline level will be subtracted from the post-dosing values and the further analysis is focused on the post-dosing changes from baseline.
- Post-dosing values that are either missing or not quantifiable will not be included in the analysis.

- Extrapolations beyond the last quantifiable plasma concentration will only be re-ported if the apparent terminal log-linearity used to this purpose is sufficiently well expressed for at least 3 data points.
- The duration of profiling is adjusted by dose; based on the available experience with rFVIII it may be expected that the quantifiable area under the time course of the concentrations (AUC) is at least 80% of the total i.e. extrapolated AUC.
- The time courses of the plasma concentrations will be summarised descriptively by means of the following non-compartmental metrics:
  - Cmax: maximum observed concentration
  - $T_{max}$ : time of occurrence of  $C_{max}$  after dosing
  - AUC(0-tz): quantifiable area under the time course of the concentrations de-rived by means of the combined linear/log-linear trapezoidal rule
  - $-\lambda_z$ : apparent terminal log-linear rate constant
  - $t_{\frac{1}{2}}$ : apparent terminal log-linear half-life
  - AUC( $t_z$ - $\infty$ ): AUC extrapolated beyond the last time point with quantifiable concentrations calculated as C\*( $t_z$ )/ $\lambda_z$  in which C\*( $t_z$ ) is the concentration at time  $t_z$  fitted according to  $\lambda_z$
  - AUC( $(0-\infty)$ ): total AUC = AUC( $(0-t_z)$ + AUC( $(t_z-\infty)$ )
  - AUCextrapolated: extent of AUC extrapolation = AUC( $t_z$ - $\infty$ )/AUC(0- $\infty$ )
  - AUMC(0-tz) and AUMC(0-∞): quantifiable and total area under the statistical first moment curve
  - MRT: mean residence time =  $AUMC(0-\infty)/AUC(0-\infty)$

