  - IVR: *in vivo* recovery = dose- and body weight-normalised maximum gain in FVIII:C
  - CL: total clearance (iv dosing only) =  $Dose/AUC(0-\infty)$
  - Vd: estimated distribution volume (iv dosing only) = CL.MRT
- Exposure levels will be reported untransformed and standardised for dose and body weight.

The same conventions will be used for the plasma concentrations of FVIII:C and OCTA12 sampled after the single dose administration of 50 IU/kg OCTA101 after the completion of the 3 months daily dosing period of Cohort 1 and Cohort 2.

Single-dose data from Cohort 3 comparing the pharmacokinetics after sc and iv dosing (Nuwiq) will be used to derive estimates of the absolute bioavailability after sc dosing and to assess route dependency of the further pharmacokinetic criteria. To this purpose, point and confidence interval estimates of the true ratio of the treatment mean for sc- relative to iv-dosing will be back-transformed from the ANOVA-derived estimates of the true difference of the treatment means of the log-transformed data. By means of a similar ANOVA, estimates of the differences of the treatment means will be derived for  $t_{1/2}$  and MRT.

Data from Cohort 5 covering the pharmacokinetics after single sc doses of 20, 40 and 60 IU/kg OCTA101 will be used to derive estimates of the dose-proportionality of the pharmacokinetics of FVIII:C and OCTA12. To this purpose, methods as described by Smith et al. (2000) will be used.

Quantifiable and  $\lambda_z$ -extrapolated time courses of the concentrations after single doses (all cohorts) will be used to simulate the time courses when defined doses would be administered

repeatedly at specified interval. To this purpose, the pharmacokinetics will be assumed to be linear i.e. dose-proportional, time-invariant and superimposable. A superposition cascade approach as described by Gibaldi (Biopharmaceutics and Clinical Pharmacokinetics – 4th edition, 1991, Lea & Febinger, Malvern, USA – Appendix II) will be used.

If the smoothness of the time courses of the concentrations permits, estimates of the absorption rate on sc dosing will be derived by the Wagner-Nelson method and/or by compartmental analysis. If appropriate, the time courses of the plasma concentrations will be analysed compartmentally, i.e. fitted to an open mammillary 1-, 2- or 3-compartmental model, and further simulations of the time courses of the concentrations on repeated dosing may be derived.

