7.2 Baseline

A baseline assessment is the last assessment prior to the first injection of OCTA101. A baseline assessment may take place on Day 1, prior to the actual sc injection.

7.3 Reference day / Day 1

The day of the first treatment with study medication OCTA101 will be Day 1 for all patients for the PK part in the study, except for Cohort 3, where the first treatment with Human-cl rhFVIII within the PK part of the study will be defined as Day 1.

Patients who enter the 3-month daily prophylactic part will be assigned a second reference day, the day of first treatment with OCTA101 during the prophylactic part.

8 Statistical analysis Specification

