8.9.1 Descriptive summaries for all cohorts

For each of the investigation periods after 20, 40, 60, 50 and 100 IU/kg sc of OCTA101 and for the investigation period after 50 IU/kg iv of Human-cl rhFVIII in Cohort 3, the concentrations of each analyte will be analyzed with geometric means, geometric coefficient of variation, arithmetic mean, standard deviation, minimum, maximum and median by time point (and visit) for the PK and PK-PP analysis set.

For each of the investigation periods after 20, 40, 60, 50 and 100 IU/kg sc of OCTA101 and for the investigation period after 50 IU/kg iv of Human-cl rhFVIII in Cohort 3, the PK parameters of each analyte (see section 5.4) will be analyzed with geometric means, geometric coefficient of variation, arithmetic mean, standard deviation, minimum, maximum and median for the PK and PK-PP analysis set.

Graphical displays of individual and of summarized data by cohort will support the summary tables.

In general, the dose-adjusted PK parameters will be determined using the "actual" dose in IU that was administered to a patient. The actual dose will be derived from the nominal dose and the actual potencies determined by the central laboratory for each batch separately.

The same analyses will be performed for the plasma concentrations of FVIII:C and OCTA12 samples and for the PK parameters of each analyte (see section 5.4) after the single dose administration of 50 IU/kg OCTA101 after the completion of the 3-months daily dosing period of Cohort 1 and Cohort 2.

These analyses will be reported in the relevant PK reports.

Summary tables of non-compartmental PK parameters of FVIII:C and OCTA12 will be additionally created for each cohort (cohorts 1, 2 and 3) and each period (cohort 5). Summary tables of plasma concentrations of FVIII:C and OCTA12 will be created by cohort and overall for all visits during the 3-months daily dosing period.

8.9.2 Bioavailability analysis for Cohort 3

Single-dose data from Cohort 3 comparing the pharmacokinetics after sc and iv dosing (Humancl rhFVIII) will be used to derive estimates of the absolute bioavailability after sc dosing and to assess route dependency of the further pharmacokinetic criteria.

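### SAP 8.9 leaves open which pre-dose level is subtracted in the repeat PK, and neither reading deals with carry-over from the daily dosing

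*SAP*

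**What the plan says.** SAP 8.9: "In the event of quantifiable levels prior to dosing, the baseline level will be subtracted from the post-dosing values". The section does not say which dosing is meant.

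SAP 7.2: "A baseline assessment is the last assessment prior to the first injection of OCTA101". SAP 7.3 adds a second reference day for the daily prophylactic part, but none for the repeat PK.

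Protocol 9.2.2 has the rule with one more word: "In the event of quantifiable levels prior to first dosing, the baseline level will be subtracted from the post-dosing values". The same list times each profile "relative to the actual time of sampling (relative to the time of first injection").

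Both documents carry these rules to the repeat PK. Protocol 9.2.2: "The same conventions will be used for the plasma concentrations of FVIII:C and OCTA12 sampled after the single dose administration of 50 IU/kg OCTA101". SAP 8.9.1: "The same analyses will be performed for the plasma concentrations of FVIII:C and OCTA12 samples and for the PK parameters of each analyte".

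Protocol 6.1.8 sets a wash-out of at least 72 h before the repeat dose of 50 IU/kg. SAP 5.2 counts 5 patients (4 from Cohort 1, 1 from Cohort 2). Protocol 3.3.1 and SAP 5.2 explain the sampling to 21 days: the initial profile was too short to show OCTA12 declining, and the later samples should allow a half-life.

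**The concern.** After about 90 daily doses and perhaps only three days off drug, the sample before the repeat dose holds accumulated OCTA12 that is still falling. The two possible baselines treat it in opposite ways.

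- **Level before the first-ever dose.** Nothing is subtracted for the carry-over. Terminal slope and half-life are unaffected, but AUC and Cmax reported after a single dose contain what is left of the daily doses.
- **Level before the repeat dose.** A decaying residue is removed as if it were constant. Late samples are over-corrected, and a log-linear slope cannot use negative values.

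At stake are the OCTA12 half-life, which was the reason for the 21-day sampling, and the meaning of the repeat-PK AUC and Cmax.

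**Working it through.** The documents give no carry-over figure, human OCTA12 half-life, absorption rate or quantification limit, so there is no stated figure to reproduce. The sizes below are ranges over assumed values.

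**1. Which baseline do the texts support?** SAP 7.2 and the word *first* in Protocol 9.2.2 favour the level before the first dose. Two things keep the other reading open. SAP 8.8.5 and 8.8.6 depart from SAP 7.2, taking laboratory and vital-sign changes "for changes from pre-dose values prior to each single injection of OCTA101". The Protocol's clock runs from the first injection, which in the repeat PK can only be that profile's own dose.

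**2. Sign of the subtracted samples, with no half-life assumed.** Protocol 9.2.2 assumes for its simulations that "the pharmacokinetics will be assumed to be linear i.e. dose-proportional, time-invariant and superimposable". Let S(a) be the level a hours after one dose and R(t) the residue of the daily doses t hours after the repeat dose. With equal doses and a 72 h wash-out:

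R(t) = S(72+t) + S(96+t) + S(120+t) + ...

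Once the earliest daily doses have washed out, R(0) - R(168) = S(72) + S(96) + S(120) + S(144) + S(168) + S(192) + S(216).

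The subtracted day-7 value is S(168) - [R(0) - R(168)] = -[S(72) + S(96) + S(120) + S(144) + S(192) + S(216)], which is below 0. The same cancellation occurs at day 14 (336 = 72 + 11 x 24) and day 21 (504 = 72 + 18 x 24). In 20,000 random single-dose shapes, all 60,000 values were negative.

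A one-compartment grid varied half-life (0.5-21 d), absorption half-life (3-48 h), number of daily doses (75-90), daily-to-test dose ratio (0.8-1.2) and wash-out. All three days were negative in 2700 of 2700 scenarios at wash-outs of 72-168 h. At 240-336 h there were 264 exceptions in 900, all with half-lives of 3 d or less.

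**3. One worked case.** Assume half-life 7 d, absorption half-life 6 h, wash-out 72 h and 90 daily doses. Units are multiples of the single-dose Cmax.

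S(t) = 1.037 x (2^(-t/168) - 2^(-t/6)); its largest sampled value is 0.874, at 24 h.

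Pre-dose level = 1.037 x 2^(-3/7) / (1 - 2^(-1/7)) / 0.874, about 9.34.

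| Day | New dose | Residue | Total minus 9.34 |
|---|---|---|---|
| 7 | 0.59 | 4.67 | -4.08 |
| 14 | 0.30 | 2.34 | about -6.7 |
| 21 | 0.15 | 1.17 | about -8.0 |

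Unsubtracted, the late samples return 7.0 d. The AUC factor is 1 + C_pre/(lambda_z x single-dose AUC). Here the single-dose AUC is 1/lambda_z on the S scale, so the factor is 1 + 9.34 x 0.874 = 9.2. Cmax is 9.7 times the single-dose value.

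**4. Half-life and exposure grid.** Half-life 1, 2, 4, 7, 14 d; absorption half-life 6, 12, 24 h; wash-out 72, 96, 168 h; 1 d with 24 h omitted: 42 scenarios at the Flow Chart 8 times.

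- Level before the repeat dose: days 7, 14 and 21 are negative in 42/42. In 30, fewer than 3 positive samples remain at or after the peak, so no half-life can be fitted. In the other 12 the fitted value is 1-75% of truth.
- Level before the first dose: half-life is within 2% of truth without noise. At 72 h wash-out AUC is 1.3-20 times and Cmax 1.4-23 times the single-dose value. MRT is 0.79-1.00 of truth across all 42.
- In the 12 scenarios with no decline by 72 h, the pattern SAP 5.2 describes, subtracting per period loses the half-life in 12/12. The first-dose reading gives AUC 3.5-20 and Cmax 4.1-23 times.

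**5. FVIII:C.** Take the minipig half-life of 25.3 h (Protocol 1.2), a 72 h wash-out and an assumed absorption half-time of 3-9 h. Subtracting per period makes the 72, 96 and 120 h samples negative and gives a half-life of 10.5-12.4 h. Unsubtracted data give 25.3-25.7 h. At 3 h absorption the pre-dose level is 0.44 of the single-dose Cmax.

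**The case against.** The strongest reply is that the documents already point to one answer. SAP 8.9 speaks of the baseline level, SAP 7.2 defines baseline, and the Protocol says *first*. The counter-evidence in SAP 8.8.5 and 8.8.6 concerns laboratory values and vital signs, not PK. On that reading the half-life survives. What remains is inflated AUC and Cmax in 5 patients, in tables that also show the high pre-dose concentration. Even on the other reading the failure would be noticed, because Protocol 9.2.2 asks for at least 3 log-linear points before extrapolating, and the raw data are kept. The SAP also follows protocol version 7.0, which is not supplied, so the missing word may be a version effect.

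Most of this stands. Loss of the half-life is a risk, not the expected result. But the favoured reading still reports multi-dose residue as single-dose exposure, so settling the wording does not settle the carry-over.

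A reader might infer more than the documents support:

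- **That the plan will report a badly shortened OCTA12 half-life.** This needs the less favoured reading and an earlier decline than the documents describe. In the scenarios that match their description the half-life is lost, not shortened.
- **That Cohort 3 bioavailability or Cohort 5 dose proportionality is biased.** The texts also name different samples there, but the dose intervals are not stated beyond a 72 h wash-out, if possible. No size can be given.

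**Conclusion.** The point holds as a misalignment between SAP 8.9 and SAP 7.2 with Protocol 9.2.2, together with the absence of any carry-over rule for the repeat PK. The sign result rests on linear superposition, roughly equal doses and wash-outs of 72-168 h. The multiples also rest on assumed OCTA12 half-lives of 1-14 d and a one-compartment model. The FVIII:C figures borrow an animal half-life. Actual wash-outs may have been longer, which shrinks the effect: at 168 h with a 1 d half-life and 6 h absorption, AUC is only 1.02 times the single-dose value. The results concerned are secondary and descriptive, in 5 patients; the primary safety endpoints are untouched. The SAP should still be corrected, because the change is cheap and neither reading gives valid single-dose exposure.

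**What to change.** In SAP 8.9 only:

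1. Name the PK baseline sample for each period (Cohort 3 iv, Cohort 3 sc, each Cohort 5 dose, repeat PK) and align the wording with SAP 7.2 and Protocol 9.2.2.
2. In the repeat PK, subtract no constant pre-dose level for either OCTA12 or FVIII:C. Estimate lambda_z and half-life from the unsubtracted late samples.
3. Report repeat-PK AUC, Cmax and MRT uncorrected for both analytes, labelled as including carry-over and not single-dose values.
4. Where a pre-dose level is quantifiable in Cohort 3 sc (FVIII:C) or Cohort 5 (OCTA12), show results with and without subtraction as a sensitivity analysis.

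Item 2 must cover both analytes. Exempting OCTA12 alone while naming the pre-repeat-dose sample as baseline would bring the error in section 5 of the working into FVIII:C.

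Cost: one paragraph and slightly more PK output, with no protocol amendment and no new samples. The downside is that repeat-PK AUC and Cmax are no longer presented as single-dose values. Individual half-lives also stay imprecise: with an assumed 15% error, one patient's OCTA12 estimate runs (5-95%) from 0.93 to 1.09 of truth at 2 d, 0.79 to 1.34 at 7 d and 0.66 to 2.07 at 14 d.
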